### **2.8 Pharmacokinetic endpoints**

Not Applicable.

### **2.9 PD and PK/PD analyses**

Not Applicable.

### **2.10 Patient-reported outcomes**

Treatment Satisfaction Questionnaire for Medication (TSQM-9) will be assessed as a PRO for the study.

The Treatment Satisfaction Questionnaire for Medication (TSQM-9) will be used to psychometrically evaluate the patients' satisfaction with Siponimod. The TSQM-9 is a sound and valid measure of the major dimensions of patients' satisfaction with medication and a good predictor of adherence across different types of medication and patient population.

With the TSQM-9, scale scores are calculated by adding the items loading on each dimension. The lowest possible score is subtracted from this composite score and divided by the greatest possible score minus the lowest possible score. This provides a transformed score between 0 and 1 that should be multiplied by 100.

Effectiveness  $([\text{Sum (Item 1 + Item 2 + Item 3)} - 3] \text{ divided by } 18) * 100$

***If one item is missing***

$([\text{Sum (Item 1 + Item 2 + Item 3)} - 2] \text{ divided by } 12) * 100$

Convenience  $([\text{Sum (Item 4 to Item 6)} - 3] \text{ divided by } 18) * 100$

***If one item is missing***

$([\text{Sum (Item 4 to Item 6)} - 2] \text{ divided by } 12) * 100$

Global Satisfaction  $([\text{Sum (Item 7 to Item 9)} - 3] \text{ divided by } 14) * 100$

***If either Item 7 or 8 is missing***

$([\text{Sum (Item 7 to Item 9)} - 2] \text{ divided by } 10) * 100$

***If Item 9 is missing***

$([\text{Sum (Item 7 and Item 8)} - 2] \text{ divided by } 8) * 100$

It should be noted that only one item may be missing from each scale before the subscale should be considered invalid for that respondent.

Change in TSQM-9 from Baseline with respect to domain scores to each post-Baseline time point will be summarized by providing: number of observations, mean, standard deviation, minimum, 25th percentile, median, 75th percentile, and maximum.

## **2.13 Interim analysis**

For the purpose of earlier dissemination, an interim analysis on the safety data will be conducted at the time of approximately 50 patients completing their Visit 5 (Day 168).

Additional interim analyses may be conducted at additional time points based on study enrollment to evaluate continued efficacy and safety data (for example, 50% enrollment). These interim analyses will also allow for an evaluation of the infusion strata.

Since there will be no hypothesis testing involved, statistical adjustment for the interim analysis will not be made at the stage of final analyses of efficacy and safety.

## **2.14 Sample size calculation**

### **Primary endpoint**

Sample size calculations were based on the rate of study drug related adverse events. During the first 6 months, such an AE rate was observed at 45% from the pooled data of patients treated with fingolimod 0.5 mg/day in studies CFTY720D2301 and CFTY720D2302. A sample size of 300 to 400 patients will provide us the precision estimates ranging from 4.9% to 5.6% precision (half-width of 95% confidence interval) of the estimated rate of AE. Of the total sample size, approximately 80-100 patients with prior infusion therapy exposure will be enrolled by balanced stratification.

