12.4.2 Statistical model, hypothesis, and method of analysis

The number (and percentage) of patients with treatment emergent adverse events suspected to be related to study medication will be summarized by primary system organ class and preferred term. The 95% confidence interval for the overall rate of adverse event suspected to be related to study medication will be calculated.

A patient with multiple adverse events within a category (overall, primary system organ class, or preferred term) is only counted once towards the total of that category.

The analysis of the primary variable will also be stratified by pre-treatment.

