### **2.5.2 Statistical hypothesis, model, and method of analysis**

The number (and percentage) of patients with treatment emergent adverse events suspected to be related to study medication will be summarized by primary system organ class and preferred term.

The 95% exact binomial confidence interval for the overall rate of adverse event suspected to be related to study medication will be calculated.

A patient with multiple adverse events within a category (overall, primary system organ class, or preferred term) is only counted once towards the total of that category.

The analysis of the primary variable will also be stratified by prior MS DMTs. Along with the overall treatment emergent adverse events suspected to be related to study medication, a subgroup analysis by prior MS DMTs will also be provided.

Analysis of primary endpoint will be based on the Safety Set.

No formal hypothesis is being tested for the primary endpoint.

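### The stated 4.9 to 5.6 point precision fits a normal-approximation interval; the exact binomial interval that the SAP specifies gives about 5.0 to 5.8 points at the same 45% rate.

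*SAP*

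**What the plan says.** The sample size sections of the two documents (Protocol 12.8.1 and SAP 2.14) carry the same text. They take the planning rate from earlier trials of another drug, where "such an AE rate was observed at 45% from the pooled data of patients treated with fingolimod 0.5 mg/day". They then state what the planned enrolment yields: "precision estimates ranging from 4.9% to 5.6% precision (half-width of 95% confidence interval"). Neither section names the interval method behind these two figures.

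The analysis sections describe the interval that will be reported. SAP 2.5.2 says: "The 95% exact binomial confidence interval for the overall rate of adverse event suspected to be related to study medication will be calculated". Protocol 12.4.2 says only: "The 95% confidence interval for the overall rate of adverse event suspected to be related to study medication will be calculated". So the SAP alone fixes the method. SAP 2.5.2 adds: "No formal hypothesis is being tested for the primary endpoint". The denominator is the Safety Set, meaning every patient who took at least one dose (SAP 2.2).

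**The concern.** With no hypothesis, margin or power, interval width is the only statistical argument offered for enrolling 300 to 400 patients. The planned precision should then describe the interval that will be reported. An exact binomial interval is usually somewhat wider than a normal-approximation interval for the same data. If the planning figures come from the approximation, the plan promises slightly more precision than its own primary analysis provides, and anyone recomputing the figure by the method in SAP 2.5.2 will not obtain the published numbers.

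**Working it through.** **Inputs.** Rate p = 0.45 (SAP 2.14, Protocol 12.8.1). Sample sizes n = 300 and n = 400 (same sections). Two-sided 95% confidence, so z = 1.96; two-sided is implied by the term half-width. Method for the primary analysis: exact binomial (SAP 2.5.2), taken here as Clopper-Pearson.

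**Step 1: reproduce the stated figures.** The Wald half-width is z × √(p(1−p)/n).

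- n = 300: 1.96 × √(0.2475/300) = 1.96 × 0.02872 = 5.63 points, which rounds to 5.6.
- n = 400: 1.96 × √(0.2475/400) = 1.96 × 0.02487 = 4.88 points, which rounds to 4.9.

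Both stated figures are reproduced.

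**Step 2: see which other methods would also give them.**

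- The Wilson half-width, z × √(p(1−p)/n + z²/(4n²)) / (1 + z²/n), is 5.59 at n = 300 and 4.85 at n = 400. These also round to 5.6 and 4.9.
- Continuity-corrected Wald (add 1/(2n)) gives 5.80 and 5.00, which does not match.
- Wald at a 50% rate gives 5.66 and 4.90, which does not match at n = 300.

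The stated range therefore fits a normal-approximation interval at 45%, either Wald or Wilson.

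**Step 3: apply the method in SAP 2.5.2.** With x events, the Clopper-Pearson limits are the 2.5% quantile of Beta(x, n−x+1) and the 97.5% quantile of Beta(x+1, n−x).

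- n = 300, x = 135: 39.28% to 50.82%. Half-width (50.82 − 39.28)/2 = 5.77 points.
- n = 400, x = 180: 40.05% to 50.02%. Half-width 4.98 points (from unrounded limits).

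Averaged over the binomial distribution of x at 45%, the exact half-width is 5.76 at n = 300 and 4.98 at n = 400, so the result does not hang on one particular count.

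**Step 4: size of the gap, unrounded against unrounded.**

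| n | Stated | Wald | Exact | Exact minus Wald |
|---|---|---|---|---|
| 300 | 5.6 | 5.63 | 5.77 | 0.14 points (about 2.5% of the Wald value) |
| 400 | 4.9 | 4.88 | 4.98 | 0.11 points (about 2.2% of the Wald value) |

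**Step 5: sensitivity to the rate.** The exact half-widths at n = 300 and n = 400 are:

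- 5.54 and 4.78 if the observed rate is 35%;
- 5.69 and 4.91 at 40%;
- 5.80 and 5.01 at 50%, where the interval is widest.

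**The case against.** The best defence is that planning with a normal approximation and reporting an exact interval is common, and that the difference here is negligible. A change of ten percentage points in the observed rate, from 45% to 35%, moves the exact half-width at n = 300 from 5.77 to 5.54. That is more than the 0.14 points in question, and the 45% itself comes from a different drug. This stands, and it is why the point is minor. It does not remove the mismatch, because both documents quote the precision to one decimal and both ends change at that decimal when the specified method is used.

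A reader might infer that the trial misses a design target, or needs more patients. The documents do not support either. They say what precision the enrolment will give; they set no maximum width and no success criterion. Searching for the smallest n at which the exact half-width at 45% is no more than 5.6 or 4.9 gives 319 and 414. That search holds unrounded widths to rounded figures, a test the Wald value of 5.63 at n = 300 also fails. Allowing widths that round to 5.6 and 4.9 brings the counts to 313 and 406. The first lies within the planned range, and no requirement makes the second necessary.

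A reader might also state as fact that Wald was used. That is an inference: Wilson rounds to the same figures, and no method is named. Nor is this the only design number, since the same sections plan 80 to 100 patients coming from infusion treatments. It is the only precision figure. Finally, the Protocol is not in conflict with itself, because its analysis section names no method; the mismatch arises against SAP 2.5.2.

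**Conclusion.** The point holds as a minor inconsistency. At the assumed 45% rate, the half-width stated in SAP 2.14 and Protocol 12.8.1 matches a normal-approximation interval, while the exact interval in SAP 2.5.2 gives 5.77 points at n = 300 and 4.98 at n = 400. The stated precision is too favourable by 0.14 and 0.11 points respectively. No decision, test or sample size depends on it.

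This rests on three assumptions: exact means Clopper-Pearson, the observed rate is near 45%, and 300 to 400 is the number of treated patients in the Safety Set. The width finally reported will follow the observed rate.

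**What to change.** In SAP 2.14 and Protocol 12.8.1, restate the precision as about 5.0% to 5.8%, and add that this is the half-width of the 95% exact binomial interval at a 45% rate. The cost is two figures and a short qualifier in each of two places, with a slightly less favourable stated precision and no extra patients.

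Leave SAP 2.5.2 and the planned 300 to 400 patients unchanged. Naming the Wilson interval there would also restore agreement (5.59 and 4.85), but it would alter a prespecified primary analysis to suit a descriptive planning figure, and nothing in the documents calls for that.

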## **3 Change to protocol specified analyses**

Not Applicable.

## **4 Appendix**

### **4.1 Imputation rules**

#### **4.1.1 Study drug**

Siponimod will be used as the study drug.

Start and end date of the study drug will not be imputed.

#### **4.1.2 AE date imputation**

##### **AE START DATE IMPUTATION (CBAF312AUS02)**

where AE start date is XX-MON-YYYY and Treatment start date is XX-TRTM-TRTY, If YYYY<TRTY and MON missing, then AE start date=1-JULY-YYYY which is prior to start of trt

If YYYY<TRTY and MON<TRTM, then AE start date=15-MON-YYYY which is prior to start of trt

If YYYY<TRTY and MON=TRTM, then AE start date=15-MON-YYYY which is prior to start of trt

If YYYY<TRTY and MON>TRTM, then AE start date=15-MON-YYYY which is prior to start of trt

If YYYY=TRTY and MON missing, then AE start date=TRTSTDT+1

If YYYY=TRTY and MON<TRTM, then AE start date=15-MON-YYYY which is prior to start of trt

If YYYY=TRTY and MON=TRTM, then AE start date=max (1-MON-YYYY, TRTSTDT +1)

If YYYY=TRTY and MON>TRTM, then AE start date=max (1-MON-YYYY, TRTSTDT +1)

If YYYY>TRTY and MON missing, then AE start date=1-JAN-YYYY

If YYYY>TRTY and MON<TRTM, then AE start date=max (1-MON-YYYY, TRTSTDT +1)

If YYYY>TRTY and MON=TRTM, then AE start date=max (1-MON-YYYY, TRTSTDT +1)

If YYYY>TRTY and MON>TRTM, then AE start date=max (1-MON-YYYY, TRTSTDT +1)

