8.1.1 Information to be collected on screening failures

[figure not shown]
All patients who have signed informed consent but not entered into the next period will have the study completion page for the screening period, demographics, inclusion/exclusion, and serious adverse event (SAE) data collected. Adverse events that are not SAEs will be followed by the investigator and collected only in the source data. For all patients who have signed informed consent and are entered into the treatment period of the study will have all adverse events occurring after informed consent is signed recorded on the Adverse Event eCRF.

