12.5 Analysis of secondary endpoints

12.5.1 Safety endpoints

Safety summaries (tables, figures) include only data from the on-treatment period with the exception of baseline data which will also be summarized where appropriate (e.g. change from baseline summaries). In addition, a separate listing for death including on treatment and post treatment deaths will be provided. In particular, summary tables for adverse events (AEs) will summarize only on-treatment events, with a start date during the on-treatment period (treatment-emergent AEs).

The on-treatment period lasts from the date of first administration of study treatment to 30 days after the date of the last actual administration of any study treatment.

Adverse events

All information obtained on adverse events will be displayed by patient.

The number (and percentage) of patients with treatment emergent adverse events (events started after the first dose of study medication or events present prior to start of open-label treatment but increased in severity based on preferred term) will be summarized in the following ways:

- By primary system organ class and preferred term
- By primary system organ class, preferred term and maximum severity
- By Standardized MedDRA Query (SMQ) and preferred term

Separate summaries will be provided for adverse events and other significant adverse events leading to discontinuation.

The number (and proportion) of patients with adverse events of special interest/related to identified and potential risks will be summarized.

A patient with multiple adverse events within a category (overall, primary system organ class, or preferred term) is only counted once towards the total of that category.

In addition, occurrence of hospitalization will be summarized using frequencies and percentages.

Vital signs

All vital signs data will be listed by patient, and visit/time and if ranges are available, abnormalities will be flagged. Summary statistics will be provided by visit/time.

In addition, change in heart rate from Baseline to 6-hour after first treatment will be summarized.

12-lead ECG

All ECG data will be listed by patient and visit, abnormalities will be flagged. Summary statistics will be provided by visit.

In addition, change in heart rate (and other vitals) from Baseline to 6-hours after first treatment, may be summarized. Please see protocol Section 8.4.2

Clinical laboratory evaluations

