### **2.7.1 Adverse events (AEs)**

The number (and percentage) of patients with treatment emergent adverse events (events started after the first dose of study medication to 30 days after the date of the last actual administration of any study treatment or events present prior to start of treatment but increased in severity based on preferred term) will be summarized.

AEs will be listed separately.

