#### AE END DATE IMPUTATION (CQVA149A2340)

AE end date = min (last visit date, last know date of contact for discontinued patients, DEC 31, date of death), if MON is missing and YYYY is present.

AE end date = min (last visit date, last know date of contact for discontinued patients, last day of the Month, date of death), if day is missing, MON and YYYY present.

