#### **4.1.3 Concomitant medication date imputation**

##### CM start date imputation

Rules for imputing the CMD start date:

Here TRTSTDT = treatment start date,

1. If the CMD start date year value is missing, the imputed CMD start date is set to TRTSTDT-1, if not after the CMD end date. Thus the imputed CMD start date = minimum (TRTSTDT-1, CMD end date).

2. If the CMD start date year value is **less** treatment start date year value, the CMD started before treatment start. Therefore:
  - a) If the CMD year is less than treatment start year and the CMD month is missing, the imputed CMD start date is set to 01JulYYYY.
  - b) Else if the CMD year is less than the treatment start year and the CMD month is not missing, the imputed CMD start date is set to 15MONYYYY.
3. If the CMD start date year value is **greater** than treatment start date year value, the CMD started after treatment start. Therefore:
  - a) If the CMD year is greater than the treatment start year and the CMD month is missing, the imputed CMD start date is set to 01JanYYYY.
  - b) Else if the CMD year is greater than the treatment start year and the CMD month is not missing, the imputed CMD start date is set to 01MONYYYY.
4. If the CMD start date year value is **equal** to treatment start date year:
  - a) If the CMD month is missing or the CMD month is equal to treatment start month, then the imputed CMD start date is set to the minimum (TRTSTD-1, CMD end date).
  - b) Else if the CMD month is less than the treatment start month, the imputed CMD start date is set to 15MONYYYY.
  - c) Else if the CMD month is greater than the treatment start month, the imputed CMD start date is set to 01MONYYYY.

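### The rule for partial adverse event start dates ignores a known end date, so some events that ended before the first dose would be counted as treatment-emergent

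*SAP*

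**What the plan says.** SAP 4.1.2 imputes partial AE start dates by comparing the recorded year and month with those of the first dose (TRTSTDT). Two branches matter here:

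- Day missing, same month and year as the first dose: "If YYYY=TRTY and MON=TRTM, then AE start date=max (1-MON-YYYY, TRTSTDT +1").
- Month missing, same year: "If YYYY=TRTY and MON missing, then AE start date=TRTSTDT+1".

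An earlier month in the same year is handled differently: "If YYYY=TRTY and MON<TRTM, then AE start date=15-MON-YYYY which is prior to start of trt". None of the start-date branches mentions the AE end date. The AE end-date rule in the same section only completes partial end dates, using the earliest of the last visit and "last know date of contact for discontinued patients, last day of the Month, date of death), if day is missing, MON and YYYY present". It does not compare the end with the start or with the first dose.

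Treatment-emergent status rests on the start date, or on worsening of an existing event. SAP 2.7.1 counts "events started after the first dose of study medication to 30 days after the date of the last actual administration of any study treatment". Protocol 12.5.1 says that "summary tables for adverse events (AEs) will summarize only on-treatment events, with a start date during the on-treatment period (treatment-emergent AEs"). Neither has a condition on the end date.

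Pre-dose events are in the database by design. Protocol 8.1.1 has, for patients who enter treatment, "all adverse events occurring after informed consent is signed recorded on the Adverse Event eCRF", and Protocol 8.1 gives a screening period of about 28 days.

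For medications, SAP 4.1.3 does use the end date: "Thus the imputed CMD start date = minimum (TRTSTDT-1, CMD end date"). It repeats that cap in the branch where the month is missing or equals the month of first dose.

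**The concern.** Moving an uncertain onset to just after the first dose is a common cautious convention in a safety study. It is only sensible while the onset really is uncertain. If the recorded end date falls before the first dose, the event was over before treatment, whatever its exact start day. The rule overrides that recorded fact. It creates a record whose start is later than its end, and it adds a false treatment-emergent event to the tables.

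Safety is the main output of this trial. Occurrence of any AE is a secondary endpoint, and the tables by system organ class, preferred term, severity and special interest are made regardless of causality. Teriflunomide patients may go through accelerated elimination during screening, and Protocol Appendix 6 itself foresees tolerability problems with that procedure. Short events that resolve before the first dose are therefore plausible, and may cluster in one prior-treatment subgroup.

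**Working it through.** **1. The same-month branch always gives Day 2.** The 1st of the month of first dose cannot be later than TRTSTDT. So max(1st of month, TRTSTDT + 1) = TRTSTDT + 1 in every case.

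**2. Rules applied to one example.** First dose 10-JUN-2021, recorded AE end 05-JUN-2021:

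| Recorded AE start | Imputed start as written | Status | Start after end? | Start with cap at end date |
|---|---|---|---|---|
| XX-JUN-2021 | max(01-JUN, 11-JUN) = 11-JUN-2021 | treatment-emergent | yes, by 6 days | 05-JUN-2021, pre-treatment |
| XX-XXX-2021 | 11-JUN-2021 | treatment-emergent | yes, by 6 days | 05-JUN-2021, pre-treatment |
| XX-MAY-2021 | 15-MAY-2021 | pre-treatment | no | unchanged |

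A start in an earlier year goes to the 15th of its month, or to 1 July if the month is missing. Both precede treatment. Complete start dates are not touched.

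**3. How much of screening is exposed.** Assume first-dose dates spread evenly over the 365 days of 2021 and onsets spread evenly over the 28 days before the first dose. That gives 365 × 28 = 10,220 combinations.

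- Day missing: the rule acts when the onset falls in the calendar month of first dose. A first dose on day d of the month has min(d − 1, 28) such onset days. These sum to 462 for a 31-day month, 434 for a 30-day month and 378 for February. In total, 7 × 462 + 4 × 434 + 378 = 5,348, and 5,348 / 10,220 = 52%.
- Day and month missing: the rule acts unless the onset falls in the previous year. That needs a first dose on 1 to 28 January and covers 28 + 27 + … + 1 = 406 combinations. So 1 − 406 / 10,220 = 96%.

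These are shares of screening-period onsets with a partial start date. Each one with a known end before Day 1 is misclassified.

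**4. Scale.** The only design figure to compare with is the precision in Protocol 12.8.1 and SAP 2.14. With a rate of 45%, 1.96 × √(0.45 × 0.55 / N) is 5.63 points at N = 300 and 4.88 at N = 400, which reproduces the stated 5.6% and 4.9%. That figure does not change.

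- One affected patient with no other treatment-emergent event adds 1/300 = 0.33 points, or 1/400 = 0.25 points, to the any-AE rate.
- Among the 80 to 100 prior-infusion patients planned, one patient is 1/80 = 1.25 to 1/100 = 1.0 points.
- At an assumed 0.5% to 2% of patients affected, the count is 1.5 to 6 of 300, or 2 to 8 of 400.
- Not all of these are new to the any-AE count, because each patient counts once. If 45% already have a drug-related event, at least 45% have some treatment-emergent event. With independence, at most 55% of those affected are new: 0.55 × 0.5 = 0.3 to 0.55 × 2 = 1.1 points.

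**The case against.** The strongest reply is about size. The rule goes wrong only when three things coincide: a partial start date, a match with the month of first dose (or its year, with the month missing), and a known end date before the first dose. AEs are collected prospectively over about four weeks, and missing values are queried before database lock (Protocol 11.2), so few such records may survive. The 0.5% to 2% has no source in the documents. All of that stands, and it limits the point to a minor one.

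The effect on the primary endpoint is also remote. The investigator would have to attribute the event to a drug not yet taken. That stands too.

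The medication rule is not a perfect model, since only two of its branches cap at the end date. But one of them is the branch for a missing or matching month, which is the counterpart of the faulty AE branches.

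Two other defences fail. Caution does not justify contradicting a recorded end date. And although SAP 2.5.3 says missing data will not be imputed, 4.1.2 gives explicit date rules that a programmer will follow. Patient listings could reveal an impossible record, but they would not correct the summary tables.

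**Conclusion.** The concern holds. Followed exactly, SAP 4.1.2 turns some AEs that ended before the first dose into treatment-emergent AEs with a start after their end, and nothing later in the plan reverses it. An oversight looks likelier than a choice: the AE end-date rules next to it carry another study's number in their heading.

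The size is small: about 2 to 8 patients of 300 to 400 under the assumed 0.5% to 2%, and at most about 0.3 to 1.1 points on the any-AE rate under the further assumptions above. It could be more visible within a small prior-treatment subgroup or a single preferred term. The textual defect is certain; its frequency is not known. The primary endpoint is unlikely to move, and the sample size is unaffected.

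**What to change.** Add to SAP 4.1.2:

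1. When the AE end date is known, the imputed start is the earlier of the rule's value and the end date.
2. An AE whose known end date is before TRTSTDT is not treatment-emergent.
3. A partial end date counts as known for this purpose if its latest possible date is before TRTSTDT, for example an end in May with a first dose in June.

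Also say how an AE ending on Day 1 is classified. The cap would place its start on Day 1, and SAP 2.7.1 is not consistent there: its definition takes events after the first dose, while its paragraph on system organ class and preferred term takes events on or after first treatment.

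The cost is one or two sentences in the SAP and a line of code before database lock. Complete dates, and partial dates whose onset is truly uncertain relative to the first dose, keep their present handling, except that a start is no longer placed after a recorded end.
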